- As-yet undetermined utilization-based variables that may help adjust for injury severity and treatment intensity (e.g., hospitalizations, number of emergency department visits in the first 6 weeks, number of provider visits, time until first opioid prescription, presence and timing of physical therapy, imaging, surgery, etc.)
- COHE and/or ECP participation may be included as an additional covariate, depending on findings from exploratory stratified analyses by COHE/ECP participation. We expect small numbers of ECP claims relative to COHE, and have no advance information on relative effect size.

The limited number of independent variables facilitates their full inclusion in the causal model, and restricts the value of propensity score techniques for this analysis topic. However, a propensity score predicting state jurisdiction (WA versus OH) will be calculated for each patient, and propensity score techniques will be used to construct comparable WA and OH samples by restricting cases to the region of common support (i.e., propensity score ranges for WA and OH will be compared, and cases above or below the overlapping range will be excluded). This approach should improve comparability of the samples, i.e., patients with covariate patterns that are typical of only one of the states will be excluded.

Subgroup analysis will be conducted in an exploratory manner. We will include interaction terms (various covariates*state) in sub-analyses to assess whether WA PA compared to OH RR has differential outcomes for particular patient subgroups (e.g., back sprain, other MSK injuries, other injury types).

Aim 1. Analysis Topic C: Compare PA to RR, using survey sample to provide more covariates

This analysis will proceed as described for Analysis Topic B, but include only the subset of the WA/OH cohorts that were included in the survey. Depending on survey eligibility and response rates, up to 100% of survey respondents may be drawn from the underlying WA/OH cohorts (however, it is possible that survey accrual may need to continue beyond cohort accrual). This will allow us to test the Aim 1 hypothesis in a sensitivity analysis that provides additional control for confounding via the inclusion of baseline survey covariates and full use of propensity score techniques, as described for Analysis Topic H below.

Aim 1. Analysis Topic D: Prescribing data validation

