Subgroup analysis will be conducted in an exploratory manner. We will include interaction terms (various covariates*state) in sub-analyses to assess whether WA PA compared to OH RR has differential outcomes for particular patient subgroups (e.g., back sprain, other MSK injuries, other injury types). We

will conduct stratified analysis for strata defined by (a) number and strength of opioid prescriptions during the acute period (0-6 weeks), and (b) continued time loss at 6 weeks.

Aim 2A

Specific aim 2A. *For injured workers in WA, examine unsafe opioid prescribing and patient-reported outcomes and work disability at 6 and 12 months for patients receiving an established, coordinated, stepped care management program during the first 12 weeks following injury plus prospective PA versus patients receiving usual care subject to PA only.*

Hypothesis 2A. *Specialized care delivered through a stepped care management program plus prospective PA will be associated with statistically significantly lower rates of unsafe opioid prescribing and improved patient outcomes compared to patients receiving usual care and PA only. [See Analysis Topics I and J]*

Aim 2A. Analysis Topic I: Compare COHE to non-COHE within WA with respect to unsafe opioid prescribing

This analysis is focused on the primary outcome for this study, unsafe opioid prescribing (defined earlier), using administrative and survey data for the full WA cohort. Our estimate is that we will have about 4,636 eligible workers in WA, and that approximately half will have an attending provider affiliated with COHE.

This analysis will test Hypothesis 2A (stated just above) with respect to unsafe opioid prescribing, using parallel analyses to those described in Analysis Topic B, and including the sensitivity analysis described in Analysis Topic C. The only adjustments are that models will include only the WA cohort, and the binary primary predictor and propensity score calculations will be based on COHE status rather than on state jurisdiction (1 for COHE, 0 for non-COHE).

Aim 2A. Analysis Topic J: Compare COHE to non-COHE within WA with respect to secondary outcomes

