We expect relatively high survey response rates, based on previous research in these injured worker populations. Barriers to recruitment include being unable to locate and contact injured workers, and injured workers choosing to not participate. The address and phone numbers of injured workers who are receiving WC benefits are largely complete and accurate because contact information is required in order to receive disability benefits. In order to increase the response rate, all eligible workers identified by WA and OH WC systems will be sent an introductory letter 1 week prior to the initiation of the phone surveys. Workers will be able to schedule a time for the survey or can opt out at that point. Workers will be paid \$50 for the baseline survey, \$30 for the 6 month survey, and \$50 for the 12 month survey (\$130 total). The University of Washington (UW) Survey Research Division (SRD) will make 10 call attempts. The SRD research staff are extensively trained in standardized interviewing techniques and methods, effective calling strategies, building rapport and interest, and refusal prevention, which all aid in minimizing attrition and maximizing response rates. The survey interviewers are trained to minimize item non-response, while supporting autonomy not to answer individual questions.

Based on these efforts, we anticipate limited amounts of missing data for individual survey items, under 5%. We do expect larger and non-negligible amounts of missing 12-month outcome data relative to 6-month outcome data on the surveys, based on projected attrition.

We will use standard techniques to identify the nature (randomness) of missing data. Where missing data are minimal (<5%) and random (no clear associations with outcomes or predictors of interest), we will use casewise deletion; we expect this approach will be adequate for administrative data and baseline survey data. For the GEE panel models testing survey-based patient outcomes, we will use multiple imputation methods, based on an expected larger amount of missing data and the likely association of missingness with previous unsafe opioid prescribing.⁴

⁴ Aloisio, K. M., Swanson, S. A., Micali, N., Field, A., & Horton, N. J. (2014). Analysis of partially observed clustered data using generalized estimating equations and multiple imputation. *Stata J*, 14(4), 863-883.

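### Topic C changes sample, covariates and propensity score use together, so its difference from Topic B cannot be attributed to better confounding control

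*Combined protocol and SAP*

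**What the plan says.** All references are to section 7 of the combined protocol and SAP unless stated.

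- **Topic B** tests Hypothesis 1 in the full Washington (WA) and Ohio (OH) cohorts. It uses a GEE logit model, a billing-data outcome and administrative covariates. The plan says that the short covariate list "restricts the value of propensity score techniques for this analysis topic", but that "propensity score techniques will be used to construct comparable WA and OH samples by restricting cases to the region of common support".
- **Topic C** follows Topic B but will "include only the subset of the WA/OH cohorts that were included in the survey". Its stated purpose is to "test the Aim 1 hypothesis in a sensitivity analysis that provides additional control for confounding". The means are the "inclusion of baseline survey covariates and full use of propensity score techniques, as described for Analysis Topic H below".
- **Topic H**, to which C points, puts the propensity score into the outcome model beside the covariates. It restricts to common support or matches only if balance requires it.
- **Topic I** carries the design into the COHE comparison, "including the sensitivity analysis described in Analysis Topic C".
- **Missing Data** plans a descriptive comparison of survey non-response, including by state. It adds post-stratification weights if differential non-response warrants them, and sensitivity analyses if indicated.

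**The concern.** Three things change between B and C: who is analysed, which covariates are used, and how the propensity score enters. The plan credits C only with better confounding control. It has no fit of the Topic B model in the survey subset and no rule for reading a B-to-C difference.

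If the odds ratio moves, confounding may have been removed, selection may have been introduced, or the subset may differ by chance. If it does not move, opposing changes may have cancelled. C is the plan's check of the primary comparison against survey-only confounders such as education, race/ethnicity, health status and baseline pain, so it matters that its result can be interpreted.

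**Working it through.** **Inputs from the plan.** Cohort: WA 4,636 and OH 779 (section 4, Enrollment/Sample Size, and Topic B). Baseline surveys: WA 3,120 and OH 525 (section 4 and Topic H). The plan gives no event rate, effect size or power figure, so there is none to reproduce. Event rates, the odds ratio of 0.70, response by outcome and covariate strength below are assumptions.

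**1. Share of the cohort in Topic C.**
- WA: 3,120/4,636 = 67.3%. OH: 525/779 = 67.4%.
- Total: 3,645/5,415 = 67.3%, so 5,415 − 3,645 = 1,770 workers (32.7%) leave.
- 67% is an upper limit. It assumes that every respondent belongs to the cohort, and Topic C allows survey accrual to outlast cohort accrual.

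**2. What selection could do.** Selection multiplies the crude odds ratio by [s(WA, unsafe)/s(WA, not)] ÷ [s(OH, unsafe)/s(OH, not)], where s is the probability of being in the survey. Take an OH rate of 10% and an odds ratio of 0.70. The WA odds are 0.70 × 0.10/0.90 = 0.0778, a rate of 7.2%. Hold overall participation at 67.3% and 67.4%.

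| Unsafe cases surveyed, WA / OH | Factor | Odds ratio in subset |
|---|---|---|
| 60% / 60% | 1.005 | 0.70 |
| 67.3% / 60% | 1.137 | 0.80 |
| 60% / 67.3% | 0.886 | 0.62 |

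For the second row, s(OH, not) = (0.674 − 0.60 × 0.10)/0.90 = 0.682, and the factor is 1 ÷ (0.60/0.682) = 1.137. The effect can be nil or go either way. It needs outcome-related participation that differs by state.

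**3. What chance alone could do.** For a random subset, Var(log OR_C − log OR_B) = Var(C) − Var(B), with Var = 1/[n_WA p_WA(1−p_WA)] + 1/[n_OH p_OH(1−p_OH)] in one window. At 10%, the standard errors are 0.132 (B) and 0.161 (C). The SD of the difference is √(0.0259 − 0.0175) = 0.092, so the 95% range for the ratio of odds ratios is 0.83 to 1.20. At OH rates of 5% and 20% the ranges are 0.78 to 1.28 and 0.87 to 1.14. The factors 0.886 and 1.137 at 10% lie inside the range.

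**4. Whether a middle fit separates the changes.** This was a simulation with 300 replicates, single-window logistic models and the plan's cohort sizes. The true conditional odds ratio was 0.70, and one survey covariate had coefficient 1 per SD. Confounding means a 0.3 SD shift of that covariate in OH. Selection means that unsafe OH cases participate 15 points less. No propensity score step was simulated.

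| Scenario | B, full cohort | B model in subset | C |
|---|---|---|---|
| Neither | 0.73 | 0.72 | 0.70 |
| Selection only | 0.73 | 0.98 | 0.95 |
| Confounding only | 0.55 | 0.55 | 0.70 |
| Both | 0.56 | 0.75 | 0.95 |

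Selection alone (0.73 to 0.95) and confounding control alone (0.55 to 0.70) both appear as an upward shift from B to C. In the first, C is the distorted result; in the second, C is the corrected one. Only the middle column tells them apart.

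**5. What the last step still mixes.** The odds ratio is non-collapsible. With a covariate balanced across states and a 10% OH rate, a marginal 0.70 becomes a conditional 0.68 (coefficient 1 per SD) or 0.61 (coefficient 2), with no confounding at all.

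**The case against.** The strongest reply has four parts.

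- **The plan already addresses non-response.** This stands in part. The comparison by state and the conditional weighting are real mitigation. However, they have no stated trigger, do not show how far the state odds ratio moves when the sample changes, and the weighting, if used, is a further difference between B and C.
- **Participation is planned before the outcome.** Baseline interviews are set for 4-6 weeks after injury. The primary composite starts at 3 months, WA's payment stop applies after six weeks and OH's chart review comes at 12 weeks. Selection could therefore act only through shared causes, some of which Topic B adjusts for. This stands, and with near-equal anticipated participation it is a reason not to presume bias.
- **Topic C is only a sensitivity analysis.** Hypothesis 1 is assigned to Topic B, and the plan never says that the B-to-C difference will be read as confounding removed. C still tests the hypothesis among respondents with more covariates. This stands and limits the weight of the point.
- **A middle fit is noisy.** This also stands (working, step 3), so the change needs an interval.

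A reader might infer that the plan itself expects survey participation to depend on the Topic C outcome, because it mentions "the likely association of missingness with previous unsafe opioid prescribing". The documents do not support that. The sentence justifies multiple imputation in panel models of survey-based outcomes. Topic C uses baseline survey covariates and a billing outcome, and the plan expects casewise deletion to be adequate for administrative and baseline survey data.

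A reader might also take the absent third to be non-respondents. It may equally include workers excluded from the survey only (section 4, Exclusion Criteria) or not approached before enrolment targets were met (section 4, Sampling Method).

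**Conclusion.** The point holds as one of attribution. Topic C, and its COHE counterpart under Topic I, differs from Topic B in sample, covariates and propensity score use, and nothing planned separates these. At most 67% of the cohort would be in Topic C, on the assumption that all respondents come from the cohort.

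It would go too far to conclude that Topic C is biased or that the primary result is in doubt. Selection affecting the odds ratio is possible, but its presence, direction and size are not shown, and every selection figure above rests on assumed response patterns. The Topic B estimate is untouched. This is a minor improvement, worth making because it is cheap and because the outcome is available for cohort members outside the survey, which is unusual for a survey-subset analysis.

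**What to change.** Pre-specify and report three fits of the same contrast, for Topic C and again for Topic I:

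1. The Topic B model in the full cohort.
2. The identical Topic B model, with the same common-support rule, in cohort members who are in the survey.
3. The Topic C model in the same complete cases as fit 2, so that missing survey items do not change the sample between 2 and 3. State whether C keeps B's common-support restriction or uses H's conditional one.

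Report the change from 1 to 2 as the effect of the change of sample. Give it a confidence interval that allows for nested samples, for example from a bootstrap or from a participation-by-state term fitted in the full cohort. Do not act on a bare difference.

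Read the change from 2 to 3 as the combined effect of added covariates and method. Preferably give it also as a standardised risk difference, because of non-collapsibility. If non-response weights are used, show fit 3 with and without them. Respondents accrued after the cohort closes stay out of this comparison.

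The cost is one extra model per comparison, on data already held.

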Enhanced Care Program (ECP), in OH. Although OH has no program entirely comparable to COHE, the OH BWC did initiate the ECP as a pilot program in 2016, to assess the effect of improving care coordination and treatment planning for injured workers with knee sprains. The pilot was established in selected counties in northeast Ohio. Providers participate on a voluntary basis and agree to use a new treatment planning form for injured workers with knee sprains and to coordinate care for those needing referral for physical therapy or specialty care. Participating providers receive 15% added payment for evaluation and management visits. The pilot is being extended during the next two years throughout OH but will remain limited to injured workers with knee sprains.

6. Outcomes

The primary outcome measure, unsafe opioid prescribing, will be measured as shown in Table 1 using pharmacy billing data from OH and WA, and validated using state PDMP data. Table 2 presents secondary outcome measures, and Table 3 presents exploratory/other outcome measures.

Table 1. Primary Outcome Measures		
Title	Description	Timeframe (after injury)
Unsafe opioid prescribing (subacute phase): Days supply	>7 days supply	6-12 weeks
Unsafe opioid prescribing (chronic phase): Chronic	≥60 days supply	3-6, 6-9, and 9-12 months
Unsafe opioid prescribing (chronic phase): Concurrent	Concurrent sedatives/hypnotics	3-6, 6-9, and 9-12 months
Unsafe opioid prescribing (chronic phase): High dose	≥50 MED/day	3-6, 6-9, and 9-12 months
Unsafe opioid prescribing (chronic phase): Composite	Meeting ≥1 of the 3 chronic-phase metrics	3-6, 6-9, and 9-12 months

MED, morphine equivalent dose.

Table 2. Secondary Outcome Measures

Title	Data Source	Description	Timeframe (after injury)
Pain intensity	Survey	PEG-3 Scale	6 weeks, 6 months, 12 months
Physical function/pain interference	Survey	PEG-3 Scale	6 weeks, 6 months, 12 months
Emotional functioning-Anxiety	Survey	PHQ-4 (Patient Health Questionnaire for anxiety and depression)	6 weeks, 6 months, 12 months
Emotional functioning-Mood	Survey	PHQ-4 (Patient Health Questionnaire for anxiety and depression)	6 weeks, 6 months, 12 months
Global improvement	Survey	Patient Global Impression of Change scale	6 months, 12 months
Disability	Survey	Does health now limit activities during a typical day	6 months, 12 months
Quality of life	Survey	EQ-5D-5L (EuroQoL-5 dimensions)	6 weeks, 6 months, 12 months

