² Penfold, R. B., & Zhang, F. (2013). Use of interrupted time series analysis in evaluating health care quality improvements. *Acad Pediatr*, 13(6 Suppl), S38-44.

³ Aloisio, K. M., Swanson, S. A., Micali, N., Field, A., & Horton, N. J. (2014). Analysis of partially observed clustered data using generalized estimating equations and multiple imputation. *Stata J*, 14(4), 863-883.

The working correlation structure will be specified as exchangeable (this may be adjusted later in the Statistical Analysis Plan), and robust variance estimates will be used. (Though using the wrong correlation structure can be inefficient, GEE is not highly sensitive to using the wrong correlation structure, as long as there are at least 100 patient clusters and robust variance estimates are used—we expect to have over 3,000 patient clusters.)

The primary predictor is binary (1 for WA cases, 0 for OH cases). The GEE logit link function will be used to test the Aim 1 hypothesis, with unsafe opioid prescribing specified as a binary dependent variable in each time window. These regression models will provide an estimate of the odds of unsafe opioid prescribing in WA compared to OH, controlling for baseline differences in the two groups. The subacute phase measure, and also each individual component of the composite measure (i.e., chronic use, concurrent sedatives, high dose), will also be tested as distinct outcomes, which will provide information on potential variation in mechanisms and timing of ORP effect across WA and OH. Time will be included in the models (assigning an indicator for quarter since the date of injury; 0, 1, 2, 3), and interacted with state in order to assess (1) change in unsafe opioid prescribing over time and (2) differences in such change by state.

Covariates will be reassessed after more information is available regarding the availability, completeness, and cross-state comparability of various data fields in the OH data. Our initial plan is to include the following covariates for this analysis topic:

- Age
- Gender
- Pre-injury wage
- Marital status
- Number of dependent children
- Injury type
- Occupation
- Industry
- Rural/urban residence
- Provider type, specialty, and COHE or ECP affiliation
- Functional Comorbidity Index (FCI) and cancer diagnosis, based on WC billing data
- PDMP data, if available (see Analysis Topic D), will be used to control for opioid prescriptions in the 3 months prior to injury

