We are in the process of confirming the feasibility of obtaining PDMP data (and specifically the payer variable) from each state for the full WA/OH cohorts and all patients included in the survey sample. Presuming we are able to obtain the necessary PDMP data, the following analyses are planned.

We will construct the various unsafe opioid prescribing variables using PDMP data, using the same methods as used for WC billing data. Further, should the payer variable be available to us, we will construct two parallel sets of outcome measures using PDMP data: (1) using all PDMP prescriptions, regardless of payer; and (2) using only prescriptions with WC as the payer. (If the payer variable is unavailable, we will construct only the first measure.) Concordance of the outcome measures by data source (and potentially with and without payer restriction) will be assessed using Cohen's kappa.

Sensitivity of findings to the data source used for the unsafe opioid prescribing outcome measures will be assessed by using the alternate measures in hypothesis tests, as described under Analysis Topics B, C, and I.

Aim 1. Analysis Topic E: Frequency and outcomes of opioid review decisions

To the extent feasible, we will document the frequency of opioid review decisions and their outcomes (patients were or were not authorized to continue using opioids beyond the respective review periods) for each state. We are investigating the existence of these data and feasibility of obtaining them from

each state. This is planned as a simple descriptive analysis (counts and percentages).

Aim 1. Analysis Topic F: Subgroup response to opioid review decisions

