As described above, version control for all incoming raw data (i.e. administrative and survey data), as well as the merged read-only analysis files, will be managed using Microsoft Excel logs of the relevant metadata. All files and folders are automatically backed up daily by the Department of Environmental and Occupational Health Sciences computing system. All data transfer and linkage procedures will meet strict Human Subjects (IRB) requirements.

For the qualitative portions of the research (i.e. individual in-depth interviews and key informant interviews), the lead qualitative analysis investigator and qualitative research assistant will be responsible for data management. Data will be stored on a secure server with backup to a separate server. Data will be de-identified after collection, and only these two individuals will have access to the key linking direct identifiers to the Study ID. Other staff responsible for analysis will only have access to the de-identified data.

Linkage of PDMP data

The linkage approach for the PDMP data may vary across states. The process in Washington is as follows:

- 1) Department of Labor and Industries (DLI) staff routinely send a list of claimant IDs and direct identifiers for WC claimants to the PDMP vendor (Appriss), on a monthly basis;
- 2) the vendor links the personal identifiers provided by DLI to PDMP records using their internal algorithms/fuzzy logic;

- 3) the vendor provides DLI with the full history of PDMP records linked to those claimants, with claimant first name, last name, and date of birth attached to each record;
- 4) DLI staff link claimant first name, last name, and date of birth in the PDMP records to the same fields in the original file sent to Appris to retrieve claimant ID; and
- 5) using claimant ID, DLI staff are able to link PDMP records to WC claim IDs and claims data for each individual injured worker.

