Thus, in Washington, PDMP data would be delivered to the research team in the same way as other WC administrative data, with claim ID available for linkage to other data files. Ohio does not yet have a routine batch delivery system in place for PDMP data, but they do have statutory authorization to receive PDMP information, and we will be working with them to set this up. However, if a similar system cannot be set up for Ohio, we will obtain data using their current mechanism, whereby Ohio Bureau of Workers' Compensation staff look up and download PDMP records for individual WC claimants, using first name, last name, and date of birth.

Data description

In addition to the logs contained in each data folder, a chronological log will be kept with any data decisions such as deleting a case or the coding of missing values. All code will be held to a documentation standard that includes a header (name of file, author, date, purpose, input data, and output data/analysis/documents) and ample documentation of all steps in the code. In addition, a data dictionary will be created that describes all of the variables used in the study including missing value coding and derived/created variables. There will be separate data dictionaries for each aim of the project.

Data storage and preservation

All raw data and analysis data sets will be stored on a secure server. Data from this server is encrypted and stored on departmental storage daily, as well as backed up daily to a different location. Offsite backup of this location occurs quarterly, with storage of up to one year. Qualitative data is similarly stored on an offsite secure server, with a separate backup server.

Data maintaining

Once the study is complete, all raw data and analysis data sets will be stored on a secure server until after the end of the applicable records retention period, as required by the University of Washington Records Management Services.

Data sharing

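### No rule separates a worker not linked to the PDMP from a worker with no opioids, and the linkage route may differ by state

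*Combined protocol and SAP*

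**What the plan says.** Section 6 measures the primary outcome "using pharmacy billing data from OH and WA, and validated using state PDMP data". Billing is therefore the main source and the PDMP the check on it.

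Analysis Topic D, which is conditional on obtaining the data, sets out the check. The outcome variables are rebuilt: "We will construct the various unsafe opioid prescribing variables using PDMP data, using the same methods as used for WC billing data". If the payer field is available there are two versions, all payers and workers' compensation (WC) payer only. Concordance with billing "will be assessed using Cohen's kappa". Sensitivity to data source is then tested "by using the alternate measures in hypothesis tests, as described under Analysis Topics B, C, and I".

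The PDMP also enters Topic B as a covariate: "PDMP data, if available (see Analysis Topic D), will be used to control for opioid prescriptions in the 3 months prior to injury". Topic H inherits the Topic B covariates, and Topic F relies on PDMP records throughout.

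Appendix A (Linkage of PDMP data) states that "The linkage approach for the PDMP data may vary across states". In Washington, "the vendor links the personal identifiers provided by DLI to PDMP records using their internal algorithms/fuzzy logic", and agency staff then re-match the returned records on name and birth date. Ohio has no routine batch delivery yet. The intention is to set one up; the fallback is for agency staff to "look up and download PDMP records for individual WC claimants, using first name, last name, and date of birth".

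The Missing Data section deals with claims, pharmacy and survey data and does not mention PDMP linkage. No section defines a linked/unlinked flag, a linkage rate, or the handling of a worker with no PDMP record.

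**The concern.** The two sources give different meanings to an absent record. Appendix A joins WC claims and pharmacy billing on claim and claimant IDs, so for a cohort member no billing record means no WC-paid fill. A PDMP record is reached through personal identifiers, so no record can mean either no dispensing or no match. A binary outcome built by the billing rules, with no missing category, cannot tell these apart. A failed match becomes a zero in every window and a zero for pre-injury use. Because it is never flagged as missing, the missing-data rules do not reach it.

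This matters because Washington's program works by denying payment. Billing alone cannot show whether prescribing fell or moved to another payer, and the PDMP re-run is the plan's only check on the outcome data source. If match rates differ by state, the misclassification is aligned with the exposure, and the re-run could agree or disagree with the billing result because of matching quality alone. In Topic F, an unlinked worker looks like someone who obtained no opioids elsewhere after coverage ended.

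**Working it through.** The documents give no linkage rate, outcome rate, effect size or power, so there is no planned figure to reproduce. Everything below except the cohort sizes is an assumption chosen to show scale.

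**Inputs.** Projected cohorts are 4,636 (WA) and 779 (OH), from Topic B. Assumed: risk p of 20% in one window, unlinked fraction u of 2% in WA and 5%, 10% or 20% in OH, and linkage unrelated to outcome.

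**1. PDMP outcome, no true difference.** If unlinked workers are scored zero, observed risk = p(1 − u). The WA/OH odds ratio (OR) is the ratio of observed odds. WA: 0.20 × 0.98 = 0.196.

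| OH unlinked | OH workers unlinked | OH observed risk | OR (true 1.00) | Chance of rejecting in that direction |
|---|---|---|---|---|
| 5% | 39 | 0.190 | 1.04 | 6% |
| 10% | 78 | 0.180 | 1.11 | 18% |
| 20% | 156 | 0.160 | 1.28 | 67% |

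Example, 10% row: (0.196/0.804)/(0.180/0.820) = 1.11. The last column is an unadjusted single-window comparison of two proportions at two-sided 0.05, with the projected cohort sizes. At a 5% outcome risk the ORs are 1.03, 1.09 and 1.24.

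**2. PDMP outcome, true OR 0.75.** With OH risk 0.20, WA odds = 0.75 × 0.25 = 0.1875, so WA risk = 0.158 and observed WA risk = 0.158 × 0.98 = 0.155. The observed OR is 0.83 with 10% of OH unlinked and 0.96 with 20%.

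**3. The reverse gap.** With linkage of 90% in WA and 98% in OH, a null OR becomes 0.90 at 20% risk and 0.91 at 5%, which favours Hypothesis 1. Equal linkage (95% in both) leaves a null OR at 1.00.

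**4. Covariate route into the primary model.** Assume a true state OR of 1.00, outcome risk of 20%, pre-injury opioid use of 20% in both states, and 2% unlinked in WA. Observed pre-injury use is 19.6% in WA against 18% in OH (10% unlinked) or 16% (20% unlinked). Fitting outcome on state and the misclassified covariate to the expected counts gives an adjusted state OR of:

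- 0.98 and 0.95 if the covariate's own OR is 3;
- 0.97 and 0.93 if it is 5.

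This shift is smaller than in step 1 and in the opposite direction.

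**5. Would kappa reveal it?** Let l be the linkage rate and let non-linkage be the only error. Observed agreement is 1 − p(1 − l), and chance agreement is p·pl + (1 − p)(1 − pl). At p = 10% and l = 90%: (0.990 − 0.828)/(1 − 0.828) = 0.94. At l = 98%, 95% and 80%, kappa is 0.99, 0.97 and 0.88. A gap large enough to bias the comparison is compatible with a kappa that would usually be reported as excellent.

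**6. After setting unlinked workers to missing.** If linkage is unrelated to outcome, the ORs in steps 1 to 3 return to their true values. The linked samples would be 4,543 in WA (4,636 × 0.98) and 740, 701 or 623 in OH.

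**The case against.** Several counter-arguments have force.

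- **Zero-scoring is an inference.** No sentence says that an unlinked worker counts as opioid-free. This stands: the defect is an unspecified rule whose literal application gives zero, not a stated wrong rule.
- **The primary result is largely insulated.** This stands for the outcome, which comes from billing. A reader might infer that the primary comparison itself is badly biased. The documents do not support that: the only route in is a covariate used if available, and step 4 puts its effect at about 2% to 3% in the middle scenario.
- **The state gap is speculative.** This also stands. Manual look-up is only Ohio's fallback, and Washington's re-match uses the same three fields. A reader might assume that Ohio will link worse; nothing in the documents shows that, and step 3 shows the bias could run the other way.
- **There are other checks.** Topic C is a separate sensitivity test of Hypothesis 1, though it changes covariates and sample and its own outcome is billing-based. A WC-payer-only PDMP measure set against billing would partly expose missed links. That depends on an uncertain payer field, and the planned summary is kappa, not specified by state.
- **Topic I is confined to Washington**, so the between-state mechanism cannot operate there. Conceded.
- **The plan calls itself tentative** and promises to reassess completeness and cross-state comparability. A data dictionary will also cover missing-value coding. These commitments are general and set no linkage check.

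**Conclusion.** The concern holds in a limited form. The plan has no rule to tell a failed PDMP match from an absence of opioids, while its own appendix says that the linkage route may vary by state. The exposed analyses are the PDMP sensitivity tests of Topics B and C, Topic F and, to a smaller degree, any model that uses the pre-injury opioid covariate. The billing-based primary outcome is not directly affected.

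The size cannot be known from the documents. Under the assumed rates, a 3-point linkage gap does little (OR 1.04 under the null). Gaps of 8 and 18 points give 1.11 and 1.28, and the direction depends on which state links better. This merits a change to the plan because the PDMP re-run is the only check on data source, kappa would not reveal the problem, and the cohort's entry rule already provides a control.

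**What to change.** Every cohort member has, by the inclusion criteria, at least one WC-paid opioid fill in the first six weeks. Use that fill as a positive control and add the following to Topic D and the Missing Data section.

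1. Class a worker as PDMP-linked if the PDMP holds a record matching the qualifying fill (same drug class, date within a few days). Report the linked share by state.
2. For workers with no linked record, set PDMP outcomes to missing, not zero. Repeat the PDMP sensitivity tests in linked workers, weighted for the probability of being linked if that differs by state. Apply the same rule in Topic F.
3. Set the pre-injury covariate to missing for unlinked workers, but impute it or use a missing indicator so that they stay in the billing-based primary model.
4. Report the billing-by-PDMP cross-tabulation and kappa by state in all workers. Give the linked-only kappa as a supplement, because restricting to linked workers selects concordant cases.

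The data are already requested. The work is fill-level matching, a weighting step and a few sentences in the plan. The PDMP analyses lose a modest number of workers (step 6 above). Some correctly linked workers whose fill was never reported to the PDMP will be classed as unlinked. The linked-only tests also assume that, given the weights, linkage is unrelated to outcome.
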